### 1.2.2 Current treatment options for patients with HR-MDS

Currently, the only curative treatment modality for patients with MDS is allogeneic hematopoietic stem cell transplantation (HSCT). Since HSCT is associated with high incidence of mortality and morbidity, only a small portion of fit patients are eligible to undergo a transplant.[\(24, 25\)](#) There is an estimate that only 6 of 100 MDS patients will receive HSCT (2 will be cured, 3 will relapse and 1 will die from the HSCT-related complications).[\(3\)](#)

Hypomethylating agents (HMAs), such as 5-azacitidine (AZA) and decitabine (DAC), are the standard of care therapies for HR-MDS. Inqovi is an oral formulation of decitabine, in combination with the cytidine deaminase inhibitor cedazuridine, which was recently FDA approved in July 2020 based on clinical trial results which showed similar drug concentrations between intravenous decitabine and oral decitabine-cedazuridine, with comparable efficacy. In the Phase 3 registrational trial for oral decitabine-cedazuridine, CR rate was 21%; additionally, 53% of patients who were RBC and/or platelet transfusion dependent at baseline achieved transfusion independence during any 56-day post-baseline period.[\(26\)](#)

Unfortunately, less than a half of patients respond to HMAs, and even the best responses are transient, non-durable, and non-curative.[\(27\)](#) Although the benefit on OS was significant in the AZA registrational trial, [\(27\)](#) in real-life practice the impact on OS is not reproducible and prolongs OS for just a few months.[\(28, 29\)](#)

Numerous combination therapies with HMAs have been explored in treatment of MDS and AML. The BCL-2-inhibitor, venetoclax, in combination with HMA has emerged as a promising therapeutic combination with good safety and efficacy in AML,[\(30\)](#) though remains under clinical investigation in MDS.[\(31-33\)](#) Two presentations on early data from ongoing clinical trials of venetoclax in combination with HMA were presented at the 2020 American Society of Hematology conference: (a) a Phase 1b trial by Garcia et al. that explored use of venetoclax plus azacitidine in 57 high-risk MDS participants, and reported an ORR of 77% with a 13 month median follow-up, and high rates of grade 3 AEs in 97% of participants, including febrile neutropenia in 46% and neutropenia and thrombocytopenia in 51% and 30%, respectively;[\(32\)](#) and (b) a Phase 1b trial of venetoclax plus azacitidine by Zeidan et al. for treatment of MDS in the relapsed/refractory setting. Of the 38 participants enrolled, with a median follow up of 6.8 months, there was a clinical response of CR + mCR in 40%, and HI in 25%. Common grade 3-4 AEs included neutropenia and thrombocytopenia in 50% and 42% of participants, respectively.[\(33\)](#) While reported efficacy is promising for this combination, the side effect profile and complications due to cytopenias appear significant based on these preliminarily data and this regimen may require further optimization in the MDS setting.

### 1.2.3 KPT-8602 (eltanexor)

#### 1.2.3.1 Selective Inhibitors of Nuclear Export (SINE)

Selective inhibitors of nuclear export (SINE) compounds directly bind and block the nuclear export protein exportin 1 (XPO1). XPO1 mediates the nuclear export of cargo proteins including tumor suppressor proteins (TSPs) such as p53, p21, and IKB, as well as eIF4E bound messenger ribonucleic acids (mRNAs) encoding oncogenic proteins such as c-MYC, Bcl-2, Bcl-SL, MDM2, and cyclin D1. As a result, XPO1 inhibition leads to nuclear retention and activation of TSPs, a reduction in the level of oncogenic proteins, and down-regulation of drug resistance and pro-inflammatory pathways. The inhibition of XPO1 by SINE compounds and subsequent nuclear

accumulation of TSPs results in selective cytotoxicity to cells with genomic damage (such as tumor cells) both *in vitro* and *in vivo*. All cell types exposed to SINE compounds *in vitro* undergo G1 and/or G2 cell cycle arrest, followed by a “genomic fidelity” review. Cancer cells with damaged genomes fail the review and undergo apoptosis. Normal cells remain in a transient, reversible cell cycle arrest until the export block is relieved. Additionally, through retention of eIF4E-bound oncogenic mRNAs in the nucleus, SINE compounds reduce oncogenic protein expression, contributing to selective induction of apoptosis in malignancies driven by these pathways.

There are 2 SINE compounds currently under clinical development for oncology indications: selinexor and eltanexor.

Selinexor (KPT-330; XPOVIO®) (34) is a first-in-class SINE compound that, in combination with dexamethasone, has regular approval from the US Food and Drug Administration (FDA) for the treatment of adult patients with relapsed or refractory multiple myeloma (MM) who have received at least 4 prior therapies and whose disease is refractory to at least 2 proteasome inhibitors, at least 2 immunomodulatory agents, and an anti-CD38 monoclonal antibody. Selinexor, in combination with bortezomib and dexamethasone, also has regular FDA approval for the treatment of adult patients with multiple myeloma who have received at least 1 prior therapy. Additionally, selinexor has accelerated approval from the FDA for the treatment of adult patients with relapsed or refractory diffuse large B-cell lymphoma, not otherwise specified (DLBCL-NOS), including DLBCL arising from follicular lymphoma, after at least 2 lines of systemic therapy. Selinexor is also currently under investigation for the treatment of various other hematologic and solid tumor indications, including further evaluation in MM, DLBCL, endometrial cancer and other gynecological malignancies, non-small cell lung cancer (NSCLC), colorectal cancer (CRC), and advanced unresectable dedifferentiated liposarcoma (DDLS), glioblastoma multiforme (GBM), and recently for patients with COVID-19. Notably, selinexor has also been investigated for the treatment of acute myeloid leukemia (AML) in 2 separate phase I trials and shown some preliminary efficacy in this setting, particularly when given in combination with decitabine.(35, 36) However, toxicity has been an issue. Selinexor can cross the blood-brain barrier (BBB). Neurotoxicity is therefore a common side effect, occurring in 25-30% of patients with MM and DLBCL in clinical trials, with severe (Grade 3-4) events occurring in 3-6%. Other common TEAEs (occurring in  $\geq 35\%$ ) reported with selinexor have included nausea (66%), fatigue (57%), anorexia (51%), thrombocytopenia (51%), anemia (44%), vomiting (39%), and diarrhea (37%).

Eltanexor (KPT-8602) is a second-generation, slowly reversible, orally bioavailable SINE compound, currently in Phase 1/2 development. It has similar potency to selinexor *in vitro* against XPO1-mediated transport and in cancer cell lines. However, it has a distinct pharmacology related to its unique chemical structure resulting in substantially lower brain penetration when compared with selinexor: ~30-fold lower in monkey studies. In animal models, this resulted in lower levels of anorexia and weight loss and permitted eltanexor once daily dosing for 5 consecutive days each week. It also exhibited superior anti-leukemic activity in *in vitro* studies of AML cell lines, and was associated with improved survival in a human xenograft model of AML. Preclinical studies also showed that eltanexor is minimally toxic to normal hematopoietic stem and progenitor cells, and eltanexor did not accumulate in plasma after repetitive dosing. The improved tolerability of eltanexor may be due to its reduced brain penetration and improved therapeutic window. The safety, tolerability, and preliminary efficacy of eltanexor is currently under investigation in Study KCP-8602-801 (hereafter referred to as Study 801, NCT02649790) which is an ongoing first-in-human, open-label dose-escalation study in patients with relapsed/refractory multiple myeloma

(R/R MM) followed by a dose-expansion phase in patients with select advanced malignancies, including mCRC, mCRPC, and HR-MDS.

#### 1.2.3.2 Dosing

As of 18 November 2023, a total of 153 patients (39 patients with R/R MM, 30 patients with RR CRC, 30 patients with mCRPC, and 50 patients with HR-MDS, and 4 with ND MDS) have received eltanexor on Study 801 and have safety data available. In addition, 3 patients have been dosed in Part F Phase 2 (HR-MDS) and 2 patients in Part G (newly diagnosed intermediate or high risk MDS in combination with Inqovi); however, no safety data is available as of the cut-off date in these 5 patients.

In the dose escalation phase, which is now complete, patients with R/R MM were dosed with 5-40 mg eltanexor daily x 5 days (5 days on, 2 days off) per week or 60 mg eltanexor every other day x 3 doses (every other day for 5 days, 2 days off), alone or in combination with dexamethasone. There were 2 DLTs observed (>4 missed doses and Grade 4 thrombocytopenia) in different dose cohorts, however, the protocol-defined MTD was not reached.[\(37\)](#) Therefore, both 20 mg and 30 mg eltanexor daily x 5 + 20 mg dexamethasone twice weekly were selected for further evaluation to clearly define the recommended phase 2 dose (RP2D).

In the dose-expansion phase, patients with mCRC were dosed at 20 or 30 mg eltanexor daily x 5, mCRPC patients were dosed at 20 or 30 mg eltanexor daily x 5 alone or in combination with abiraterone, and HR-MDS patients were dosed at 10 or 20 mg eltanexor x 5 (5 days on, 2 days off, in 28-day cycles).

In patients with HMA-refractory HR-MDS (n = 35) treated with single-agent eltanexor, the median duration of eltanexor (10 mg) was 19.1 weeks (range 2 to 85); however 10 patients treated for  $\geq$  24 weeks. In 10 mg cohort (n = 5), 3 patients (60%) had marrow complete response (mCR) and 2 patients (40%) had stable disease (SD). In the 20 mg cohort (n = 10), 4 patients (40%) had mCR and 3 (30%) had SD. The overall survival (OS) for all patients was 9.9 months, and 11.9 months for those achieving mCR vs 8.7 months for those who did not achieve mCR (hazard ratio = 0.27, p=0.05). [\(38\)](#)

In the entire safety population, the most frequently occurring TEAEs of any grade were nausea (56.9%), fatigue (64.1%), diarrhea (54.9%), decreased appetite (43.8%), thrombocytopenia (45.8%), weight decreased (42%), neutropenia (42.5%), anemia (38.6%), vomiting (38.6%), and constipation (30.7%). The most frequently occurring  $\geq$  Grade 3 TEAEs were thrombocytopenia (31.4%), anemia (25.5%), and neutropenia (32.7%). However, no clinically significant cumulative toxicities were identified, major organ dysfunction was not observed, and no grade 5 TRAEs were reported. Adverse events leading to discontinuation of eltanexor that occurred in  $\geq$  3 patients were fatigue (5%), nausea and acute kidney injury (3.4% each), sepsis and weight decreased (2.5% each). There was one patient that did not have a TEAE.

In the MDS cohort (n = 20), the most frequently occurring TEAEs of any grade were diarrhea (70%), nausea (60%), dyspnea (50%), abdominal pain (45%), fatigue (45%), anemia (40%), constipation (40%), dizziness (40%), weight decreased (35%), neutropenia (35%), leukopenia (30%), and thrombocytopenia (30%). The most frequently occurring  $\geq$  Grade 3 TEAEs were anemia (40%), neutropenia (30%), and thrombocytopenia (30%). However, all AEs were reversible and manageable by supportive care and dose modification, and no grade 5 TRAEs were reported. [\(39\)](#) See the Eltanexor Investigator's Brochure (IB) for more information.

Clinicians typically underestimate the symptoms of the toxic effects or adverse events experienced by patients.[\(40, 41\)](#) Patient-centered outcomes assessment starts with an understanding of the impact of a disease and its treatment on patients, and what patients value from a treatment perspective. In cancer-related clinical trials, regulatory agencies and advocacy groups increasingly encourage using patient-reported outcomes (PROs) to describe the clinical benefit of a therapeutic regimen. This includes using information on disease-associated symptoms or functions to help determine treatment efficacy and understand treatment-associated side effects. These measures, which collect information directly from the patient, without interpretation by somebody else, improve researchers' understanding of the patient perspective on the treatment's impact. Standardizing and incorporating PROs into earlier phase trials such as this dose finding in re-irradiation would allow them to be optimized, improve study design and allow more rigorous and systematic assessment of PROs in later-phase trials.

Tolerability and efficacy for KPT-8602 in HR-MDS are being further studied in the Phase 2 portion of Study 801 along with a Phase 1b study in AML. Additional studies in both solid tumors and hematological malignancies are planned. Phase 1 evaluation is also ongoing in newly diagnosed intermediate or high risk MDS.

Additionally, preclinical studies have exposed various dosing strategies for KPT-8601 including 5 days/week and continuous daily dosing, and have suggested that either strategy is feasible [\(42, 43\)](#).

#### 1.2.3.3 Pharmacokinetic (PK) and pharmacodynamic (PD) data

In Study 801, the PK profile of KPT-8602 (eltanexor) after oral administration was predictable, dose-proportional, and exhibited moderate inter-patient variability across doses of 5-20 mg in male and female patients with R/R MM, mCRC, mCRPC, and HR-MDS. Following single doses of 5-60 mg at C1D1, the eltanexor PK profile was characterized by rapid absorption (median  $T_{max}$  1-3 hours) and moderate clearance (21-35 L/h), volume of distribution 170-264 L, and terminal half-life 4-6 hours. Interindividual variability was moderate as evidenced by geometric mean percent coefficient of variation (%CV) values (range) for  $AUC_{0-\infty}$  24-44% and  $C_{max}$  15-53% (Eltanexor IB, version 4.0).

[figure not shown]
Based on nonclinical and exploratory clinical data from SINE compounds, the change in XPO1 mRNA expression after treatment is an appropriate PD marker and was used to evaluate target engagement across the first 6 R/R MM cohorts treated with single-agent eltanexor on Study 801. Target engagement was assessed from whole blood collected on C1D1 at 2, 4, 8, and 24 hours post dose of eltanexor and was compared to the relative level (i.e., set to 1 at 0 hrs) at pre-dose. The plasma concentration of eltanexor was also calculated and plotted. For all cohorts evaluated, the fold-change maximum ( $F_{max}$ ) of XPO1 mRNA expression was achieved 4 to 8 hours post-dose. The  $F_{max}$  and  $AUC_{24}$  for XPO1 mRNA was roughly dose proportional to the  $C_{max}$  and  $AUC_{24}$  of eltanexor in plasma samples from these patients. The plateau for  $F_{max}$  and  $AUC_{24}$  of XPO1 mRNA in treated patients was 5-fold change and 100-fold change (baseline\*hr), respectively, when compared with pre-dose levels. Based on these preliminary data, the maximum dose for these XPO1 changes occurs in patients treated with 60 mg of eltanexor. Although the RP2D of 20-30 mg eltanexor (depending on the indication) does not maximize the  $F_{max}$  at C1D1, this reduced response of XPO1 mRNA may correlate with the improved tolerability of eltanexor. Of note, there is currently not enough data for a clinically reliable marker of maximal pharmacologic activity for eltanexor. We will use the MTD to make our RP2D determination and use the totality of data from

this early phase trial, including PK, PD, safety and MTD interpretation to best determine optimal dosing in later trials.

#### 1.2.3.4 Rationale for combining KPT-8602 (eltanexor) and Inqovi

DNMT3B is one protein responsible for *de novo* DNA methylation and fast rebound methylation after HMA cessation in MDS. The proto-oncogene c-MYC directly binds the DNMT3B promoter, causing increased expression of DNMT3B. By interfering with c-MYC translation, KPT-8602 may diminish rebound methylation after decitabine cessation and improve treatment responses in patients with MDS (Figure 1). Preliminary reports from Study 801 show anti-tumor activity and an acceptable toxicity profile for KPT-8602 in patients with HR-MDS who have failed HMAs. Additionally, preclinical studies have shown that decitabine priming increases antileukemic effects of selective inhibitors of nuclear transport (SINEs) in AML *in vitro* and *in vivo*. (44) Therefore, sequential addition of KPT-8602 to Inqovi may further improve treatment responses in participants with myeloid malignancies by acting synergistically to inhibit further DNA methylation.

**Figure 1: Synergy between eltanexor (KPT-8602) and decitabine**

Abbreviations: DAC, decitabine; Elta, eltanexor; TSP, tumor suppressor protein  
Figure provided by [name], NCI

#### 1.2.3.5 Rationale for Myeloid Malignancy Program Investigation

In general, long term treatment outcomes for MDS patients are dismal. It is estimated that of every 100 MDS patients, 4 will be long-time survivors, with the rest of succumbing to either MDS- or treatment-related complications (67) or MDS-unrelated complications (29). (3) There has been no progress in populations based studies in survival of MDS patients during last 2 decades. (29) Novel approaches are needed which do not rely exclusively on cytotoxic therapy and/or intervene earlier in the course of the disease. Current clinical trials for participants with MDS enroll less than 5%

of MDS patients.(28) With better understanding of complex MDS pathophysiology, trials using combination treatments are emerging, especially for those ineligible for HSCT.(11)

A new Clinical and Translational Correlates Facility was recently funded by the *FY20 Directors Challenge Innovation Award* and is physically housed initially within NHLBI space (PI [name] *et al*). This facility will create the ability to perform standardized research correlates proposed on this study and across the growing NIH Myeloid Malignancies Clinical Trials portfolio. Work from intramural investigators has recently demonstrated that high-sensitivity genomic measurements outperform conventional clinical assessments for myeloid malignancy participants in predicting relapse and survival following HSCT and suggest that additional intervention on high-risk subjects can improve clinical outcomes.(45) This sets the stage for a “precision medicine” approach where personalized assessments of clonal disease burden can be used not only to judge the success of therapy, but also as a target for intervention.

In this trial, we hypothesize that sequential addition of KPT-8602 (eltanexor) to Inqovi is safe in treatment of adult MDS participants. For the phase 2 trial, we hypothesize that eltanexor enhances the efficacy of Inqovi in adult MDS participants.

## 2 ELIGIBILITY ASSESSMENT AND ENROLLMENT

### 2.1 ELIGIBILITY CRITERIA

#### 2.1.1 Inclusion Criteria

2.1.1.1 Participants must have histologically or cytologically confirmed MDS by the Laboratory of Pathology, NCI- according to 2016 WHO criteria(1)

AND:

- Cohort 1 (Phase 1) & 2 (Phase 2): have HR-MDS (IPSS-R > 3.5) with inadequate response to hypomethylating agent (HMA) therapy [(received  $\geq$  4 cycles of the standard dose (35 mg decitabine and 100 mg cedazuridine) without prior dose-reductions, with failure to achieve at least a PR or experienced disease progression prior to completing 4 cycles)

2.1.1.2 Age  $\geq$ 18 years

2.1.1.3 ECOG performance status  $\leq$  2 (Karnofsky  $\geq$  60%, see [Appendix A](#))

2.1.1.4 Participants must have adequate organ and marrow function as defined below:

- total bilirubin  $\leq$  1.5 X institutional upper limit of normal

OR

$\leq$  3 X institutional upper limit of normal in participants with Gilbert’s syndrome (except for participants with increased bilirubin levels attributed to intramedullary hemolysis, which will be allowable)

- AST(SGOT)/ALT(SGPT)  $\leq$  3 X institutional upper limit of normal

OR

	≤ 5 X institutional upper limit of normal if related to MDS-specific cause
• creatinine clearance (by Cockcroft-Gault)	≥ 60 mL/min/1.73 m 
• QTc(F)	≤ 470 ms

2.1.1.5 Individuals of child-bearing potential (IOCBP) must have a negative serum test at screening. IOCBP is defined as the following:

- Has not undergone a hysterectomy, tubal ligation, or bilateral oophorectomy
- Has not been naturally postmenopausal for at least 24 consecutive months (i.e., has had menses at any time in the preceding 24 consecutive months).

2.1.1.6 Individuals of childbearing potential (IOCBP) as well as those able to father a child with an individual able to become pregnant must agree to use adequate contraception (hormonal or barrier method of birth control; abstinence) unless they have had a prior vasectomy, hysterectomy, or bilateral oophorectomy, prior to study entry, for the duration of study participation, and for at least 6 months after last dose of HMA.

2.1.1.7 Breastfeeding participants must be willing to discontinue breastfeeding from study treatment initiation through 30 days after the last administration of study drug

2.1.1.8 Any prior therapy must have been completed >4 weeks or, if known, ≥ 5 half-lives of the prior agent (whichever is shorter) prior to treatment (with a minimum of 1 week between prior therapy and study treatment). Note: This does not apply to prior HMA therapy if that therapy is Inqovi per Section 2.1.1.1.

2.1.1.9 Ability to understand and the willingness to sign a written informed consent document.

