### 3.3.1 Dose Levels for Toxicity Management

Dose levels for KPT-8602 (eltanexor) are as follows, for the purposes of toxicity management.

•

Dose level	KPT-8602 dosage
2	10 mg orally once daily on Days 8-21
1	10 mg orally once daily on Days 8-12 and Days 15-19
-1	5 mg orally once daily on Days 8-21
-2	5 mg orally once daily on Days 8-12 and Days 15-19

Dose levels for Inqovi are as follows, for the purposes of toxicity management.

•

Dose level	Inqovi dosage
1	1 tablet orally once daily on Days 1 through 5
-1	1 tablet orally once daily on Days 1 through 4
-2	1 tablet orally once daily on Days 1 through 3
-3	1 tablet orally once daily on Days 1, 3, and 5

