### **3.7.2 Off-Study Criteria**

- Off treatment and completed follow-up on study (i.e., all participants will be followed for 8 years, or until death, whichever comes first)
- Participant requests to be withdrawn from study
- Death
- Screen failure
- Lost to follow-up
- Study is cancelled for any reason

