### 6.3 RESPONSE CRITERIA

Participants will be assessed for response by standard response criteria for MDS.[\(54\)](#) For the purposes of this study, participants will be re-evaluated for response after each cycle by CBC with differential to assess for improvement in cytopenias and by protocol-defined time points for bone marrow evaluation. If results from bone marrow assessment and/or CBC demonstrate progression of disease (as defined by an increase in the number of malignant cells or blasts when compared to pre-treatment bone marrow examination or worsening cytopenias by amounts as defined below in section [6.3.1](#)), the participant will be taken off treatment. However, the participant will continue to be followed on study for other survival endpoints.

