**Chemical structure:**

5-Pyrimidineacetamide,  $\alpha$ -[[3-[3,5-bis(trifluoromethyl)phenyl]-1*H*-1,2,4-triazol-1-yl]methylene]-, ( $\alpha$ *E*)-(*E*)-3-(3-(3,5-bis(trifluoromethyl)phenyl)-1*H*-1,2,4-triazol-1-yl)-2-(pyrimidin-5-yl)acrylamide

- **Molecular weight:** 428.30 g/mol
- **Mechanism of action:** selective inhibitor of nuclear export (SINE)

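### Criterion 2.1.1.6 counts the 6-month contraception period from the last HMA dose and omits KPT-8602, so individuals of childbearing potential who leave the study early can fall short of 6 months after the drug taken last

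*Combined protocol and SAP*

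**What the plan says.** Criterion 2.1.1.6 (Section 2.1.1) applies to individuals of childbearing potential and to those able to father a child. It asks for contraception "for the duration of study participation, and for at least 6 months after last dose of HMA". The only HMA in the regimen is Inqovi. KPT-8602 is described in Section 14.1 as a nuclear export inhibitor, and 2.1.1.6 does not name it.

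Other sections bear on the same rule:

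- Section 8.6.2 tells male participants not to father a child or donate sperm during the study and for 6 months after KPT-8602 or Inqovi.
- Section 8.6.1 gives no contraception period for women. It follows pregnancy outcomes until 6 months after the last study drug.
- Section 12.1 justifies contraception by both drugs: Inqovi is a known teratogen, and the fetal effects of KPT-8602 are unknown.
- Study participation is not defined. Section 3.7.2 says "all participants will be followed for 8 years, or until death, whichever comes first", and Section 6.3 says that after treatment stops for progression "the participant will continue to be followed on study for other survival endpoints".
- Section 3.7.2 also lists routes off study, among them "Participant requests to be withdrawn from study", loss to follow-up, and "Study is cancelled for any reason".

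**The concern.** The post-dose period runs from the drug given first in the cycle. Inqovi is given on Days 1-5 and KPT-8602 from Day 8, so in a normal final cycle the HMA-anchored 6 months ends before 6 months have passed since KPT-8602. Section 3.3 also lets KPT-8602 continue when Inqovi is stopped or delayed, which widens the interval.

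For men, 2.1.1.6 and 8.6.2 give different starting points, but observing the later one satisfies both. For participants who can become pregnant, 2.1.1.6 is the only contraception period counted from a dose. The calendar in Section 3.5.2 shows pregnancy tests on Day 1 of later cycles and none at the End of Treatment visit. After treatment, this rule is therefore the main remaining safeguard. At stake is a consistent safety instruction; no estimate or test depends on it.

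**Working it through.** The plan states no shortfall, so there is no figure to reproduce. The check is day arithmetic.

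**Inputs**

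- KPT-8602 levels 1 and -2 run to Day 19; for example, level 1 is "10 mg orally once daily on Days 8-12 and Days 15-19" (Section 3.3.1). Levels 2 and -1 run on Days 8-21.
- The last Inqovi dose is on Day 5 at full dose and at level -3 (Days 1, 3 and 5), on Day 4 at level -1, and on Day 3 at level -2 (Section 3.3.1).
- Cycles last 28 days.
- Benchmark: 6 months after the last dose of either drug, as Section 8.6.2 sets for men.
- Assumptions: 6 months is 183 days, and there are no missed-dose extensions.

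**Formula**

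Shortfall = 28k + (last KPT-8602 day - last Inqovi day), where k is the number of final cycles with KPT-8602 but no Inqovi.

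| Final dosing | KPT-8602 stops Day 8 | Last dose Day 19 | Last dose Day 21 |
|---|---|---|---|
| Both drugs, Inqovi to Day 5 | 8 - 5 = 3 | 19 - 5 = 14 | 21 - 5 = 16 |
| Both drugs, Inqovi to Day 4 | 8 - 4 = 4 | 19 - 4 = 15 | 21 - 4 = 17 |
| Both drugs, Inqovi to Day 3 | 8 - 3 = 5 | 19 - 3 = 16 | 21 - 3 = 18 |
| Full-dose Inqovi, then one KPT-8602-only cycle | 28 + 3 = 31 | 28 + 14 = 42 | 28 + 16 = 44 |
| Full-dose Inqovi, then two KPT-8602-only cycles | 56 + 3 = 59 | 56 + 14 = 70 | 56 + 16 = 72 |

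**Who is affected**

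The first limb of 2.1.1.6 covers a participant for as long as participation lasts. If that includes follow-up, someone still on study 6 months after the last KPT-8602 dose has no gap. Someone who leaves before the HMA-anchored period ends has the full shortfall in the table. Someone who leaves between the two end dates has part of it. If participation means treatment, the full shortfall applies to everyone in this group whose last dose was KPT-8602.

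**What the shortfall means for exposure**

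Section 1.2.3.3 reports rapid absorption, moderate clearance "and terminal half-life 4-6 hours". After a completed two-drug cycle with full-dose Inqovi, 183 - 16 = 167 to 183 - 14 = 169 days of cover remain after the last KPT-8602 dose. At the slowest stated half-life, 167 x 24 / 6 = 668 half-lives. After one completed KPT-8602-only cycle, at least 183 - 44 = 139 days remain, or 139 x 24 / 6 = 556 half-lives.

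**After the fix**

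Counting from the later of the two last doses makes the shortfall 0 days in every row.

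**The case against.** The strongest reply is that the criterion already covers these participants. Its two limbs are cumulative, and the protocol separates leaving treatment (3.7.1) from leaving the study (3.7.2). Follow-up lasts up to 8 years, and Section 6.3 treats people off treatment as still on study. On that reading, nobody who stays in follow-up has a gap. This largely stands, and it makes the treatment-only reading the weaker one. But the term is undefined, and on the broad reading the 6-month clause adds nothing for anyone who stays on study. Its work is then confined to withdrawal, loss to follow-up and study cancellation, which are the cases where it runs short.

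Secondly, no section requires 6 months of contraception after KPT-8602 for women, and tying the period to the known teratogen could be deliberate. It is true that the benchmark is borrowed from 8.6.2. However, 12.1 rests contraception on both drugs, and no reason is given for a narrower rule for participants who can become pregnant than for men.

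Thirdly, the consequence is slight. This stands. The half-life is short, the bacterial mutation test was negative (14.1.3), and about 80% of MDS patients are 65 or older (1.2.1). Against that, adults from 18 are eligible, and Section 5.2.8 notes that XPO1 inhibition increases DNA damage in cells, so plasma clearance is not the only consideration.

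A reader might infer more than the documents support:

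- *That men are left uncovered.* Section 8.6.2 covers them; for men the issue is only that two sections differ.
- *That 3 to 16 days is the whole range.* It holds only for a two-drug final cycle with full-dose Inqovi.
- *That the longer gaps are typical.* A KPT-8602-only cycle needs toxicity attributed solely to Inqovi or a start-of-cycle delay of Inqovi alone (3.3), and the stepwise reductions in 3.3.2.1 discontinue KPT-8602 before Inqovi.
- *That meaningful fetal exposure follows.* The stated pharmacokinetics do not suggest it.

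**Conclusion.** The point holds as a minor wording and consistency defect with a small safety component. Criterion 2.1.1.6 omits the investigational drug from the only dose-anchored contraception period for individuals of childbearing potential, and it disagrees with 8.6.2. The gap arises on early study exit, or if study participation is read as treatment.

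The sizes in the table rest on the 6-month benchmark of 8.6.2, 28-day cycles and no missed-dose extensions. The day differences do not depend on how 6 months is converted to days; the days of cover remaining and the half-life counts do. Few participants are likely to be affected. Sample size, error rates and analysis are unchanged. The consent pages are not in the copy reviewed, so it cannot be said what period participants are actually told.

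**What to change.** In 2.1.1.6, replace the HMA anchor so that the 6 months runs from the last dose of KPT-8602 or of Inqovi, whichever is later. If the consent form repeats the HMA-only period, change it in the same way. Adding the same whichever-is-later wording to 8.6.2 is optional, since that section already names both drugs.

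The cost is a wording change in the next amendment, with no extra visits, tests or participants.
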